#### **10.5 Procedures**

The participants are to be selected from the communities located in different regions in Wuhan by convenient sampling. The participants joined the cross-sectional study conducted by principal investigator in 2018 will be first invited. The staff working in community centers will also send notice to the residents' online chat room. Every potential participant will have a trained research assistant responsible for explaining the RCT details with the information sheet (Appendix 3) and re-assuring the respondents that data collected in the study will be kept strictly confidential, and then seeking permission for conducting the screening. The potential participants will be screened according to inclusion and exclusion

[figure not shown]
criteria (Appendix 4). The eligible participants will sign the written consent (Appendix 5) and accomplish the baseline questionnaire and assessments (T0). After that the participant will be randomly divided into intervention group or control group.

Block randomization method will be used (Kang, Ragan, & Park, 2008). The investigator will randomly select block sizes such as two, four, or six, to make randomization sequences for 156 participants. Then randomization sequences will be printed and placed in a sequentially numbered opaque sealed envelope. After older adult sign consent and finishing the baseline questionnaire and assessments, the researcher will open the envelop according to the numbered sequence for the grouping allocation.

The intervention group will receive kyphosis-specific exercise class, kyphosis-specific exercise video and a log book (sample page is shown in Appendix 6). Before every exercise class, the researcher will send them time and location as reminders. Class attendance is recorded every time. The participants are asked to record the time of home kyphosis-specific exercise practice and other daily exercises. They can also write down questions about kyphosis-specific exercise in the log book. The investigator will check the log book and respond to the questions once a week. The Control group will receive a booklet introducing general health education material, and a log book recording the time of daily exercises (sample page is shown in Appendix 7).

After the end of 6 weeks intervention, all participants will be invited to finish the postintervention assessment (T1). The flowchart of the proposed RCT is presented in Figure 1.

**Figure 1** The flowchart of proposed RCT

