## **11. Describe any unusual or discomforting procedures to be used**

Exposing the upper body in spine measurement may be embarrassing for some participants. In order to protect their privacy, the participant will be invited to a private room with air-conditioned, one at a time. The principal investigator and well-trained researcher helpers will perform the measurement. And the participants can stop measuring whenever they want to. For the measurement of physical fitness, participants may be tired. They can take a rest whenever they need.

In kyphosis-specific exercise class, the instructor participants ratio will be no less than 1:5 to endure the participants' safety. During exercise class, the participants can rest whenever they think is necessary. The first aid equipment will

be prepared. In the video exercise group orientation, the investigator will give exercise safety instruction.

Most of the exercises including in the kyphosis-specific exercise video are taking supine or prone posture, in order to prevent fall during exercise. In every follow up kyphosis-specific exercise classes, the certified physical trainer will reinforce safety instructions and exercise skills. The participants will be encouraged to contact the investigator whenever they have questions. No serious adverse event was reported by the previous studies letting older adults following exercise video doing home exercise.

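### The person who makes the randomization list appears also to measure the primary outcome, so sealed envelopes alone do not secure concealment or assessor blinding

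*Combined protocol and SAP*

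**What the plan says.** All of this is in the combined protocol and SAP.

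- **List.** Section 10.5: "The investigator will randomly select block sizes such as two, four, or six, to make randomization sequences for 156 participants". No statistician, off-site service or other independent person is named as maker or holder of the list.
- **Concealment.** Section 10.5: "Then randomization sequences will be printed and placed in a sequentially numbered opaque sealed envelope". Allocation comes late, once consent and the T0 assessments are complete. At that point, "the researcher will open the envelop according to the numbered sequence for the grouping allocation".
- **Approach to candidates.** Section 10.5: "Every potential participant will have a trained research assistant responsible for explaining the RCT details with the information sheet". Who judges eligibility is not stated.
- **Measurement.** Section 11, on the spine measurement: "The principal investigator and well-trained researcher helpers will perform the measurement". Section 6.1 makes this angle the primary outcome, and the statistical section analyses its change.
- **Contact during the trial.** Section 10.5, on the intervention arm: "The investigator will check the log book and respond to the questions once a week".
- **Blinding.** Section 10.1 calls the trial single blinded. Participants and the exercise instructor know the arm; those who carry out the assessments are meant not to.

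**The concern.** Sealed numbered envelopes hide the next allocation from someone who has not seen the list and cannot infer it. They hide nothing from the person who wrote it. If that person also measures the spine, two protections weaken together.

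The first is concealment at entry. Sampling is by convenience, and people from the principal investigator's 2018 cross-sectional study are approached first, so the team has some control over the order of entry. Eligibility depends on hand-taken inclinometer readings: an angle above 40° and the ability to reduce it by 5°. Foreknowledge of the next arm could affect who is put forward next and how the T0 angle is read.

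The second is assessor blinding. The same foreknowledge applies at T1. Because the primary outcome is a change in angle, a reading shifted at either visit passes straight into it. Bias of this kind cannot be reliably removed in the analysis.

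**Working it through.** The plan gives no predictability figure to reproduce. The check has two parts: who holds which role, and how much can be foreseen without the list.

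**1. Roles side by side**

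| Task | Who, as written | Section |
|---|---|---|
| Makes the sequences | The investigator | 10.5 |
| Holds the list | Not stated | – |
| Explains the trial | A trained research assistant | 10.5 |
| Opens envelopes | The researcher | 10.5 |
| Checks log books weekly | The investigator | 10.5 |
| Measures the spine angle | The principal investigator and helpers | 11 |
| Must be blinded | Those who assess | 10.1 |

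Are the investigator and the principal investigator the same? The protocol never says so outright. But section 7 credits the systematic review once to the investigator and later to the principal investigator, so the two terms appear to name one role. On that reading, the first and sixth rows are the same person, and the last row cannot be assured. Section 11 does not limit the principal investigator's measuring to one visit, so it can cover both T0 and T1.

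**2. What can be foreseen**

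Inputs: 156 allocations; two arms at 1:1 (implied by 78 per group in 10.4); block sizes 2, 4 and 6 (10.5). Assumption: the sizes are equally likely, since no probabilities are given.

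*Holder of the list:* 156/156 = 100%, whatever the sizes.

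*Someone who knows the length of each current block.* In a block of size 2m, the expected number of forced allocations is 2m/(m+1):

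- size 2: 2/2 = 1
- size 4: 4/3 = 1.333
- size 6: 6/4 = 1.5
- size 8: 8/5 = 1.6

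The forced share of a mixture is the mean number forced divided by the mean block size:

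- 2/4/6: (1 + 1.333 + 1.5)/3 = 1.278; 1.278/4 = 31.9%; × 156 ≈ 50 allocations
- 4/6: (1.333 + 1.5)/2 = 1.417; 1.417/5 = 28.3%
- 4/6/8: (1.333 + 1.5 + 1.6)/3 = 1.478; 1.478/6 = 24.6%

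*Someone who knows the possible sizes and every past allocation, but not the current block's length.* Lists of 156 were simulated (1,500 per scheme). An optimal guesser updated the probabilities of block size and position after each allocation:

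| Sizes | Correct guesses | Certain in advance | Certain, of 156 |
|---|---|---|---|
| 2/4/6 | about 70% | about 4% | about 6 |
| 4/6 | about 69% | 5.5–5.7% | about 9 |
| 4/6/8 | about 68% | 2.3–2.4% | about 4 |

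The ranges reflect simulation error. Chance is 50%, or 78 of 156; 70% is 0.70 × 156 ≈ 109.

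**3. Reading**

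Changing the sizes moves the guess rate by about two percentage points, and simply dropping size two slightly raises the number of certain allocations. Taking the list away from a measurer brings that person down from 100% to, at worst, the values in the last table.

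**The case against.** The other side has a fair case, and several parts of it stand.

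- *The trial is not unblinded.* A reader might infer this because arms are visible to participants and instructor. Section 10.1 describes a single-blind design with blinded assessors. The point is that the task assignments undercut that statement, not that blinding was never planned.
- *Small blocks do not make a third or a half of allocations certain.* The 32% needs knowledge of each current block's length. Sizes are chosen at random and given only as examples, so about 4% is the better figure without the list. Half would be certain only if a single size of two were used throughout and became known. The text could be read as one draw for the whole list, but it does not say so.
- *The overlap of roles is inferred.* The list-maker is not expressly the principal investigator. Nothing says the list-maker enrols, since a research assistant explains the trial and a researcher opens envelopes. Nor does the text say that the list is kept or consulted after the envelopes are filled.
- *The envelopes are sound procedure.* Opening them only after consent and T0 protects well against anyone without the list.

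What this does not answer is the gap itself: nothing in the protocol separates the list-maker from measurement, and the natural reading joins them. The plan can be followed exactly as written while a blinded assessor holds the whole sequence.

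**Conclusion.** The point holds as a weakness in the separation of roles, and it is minor in the effort needed to cure it. As written, the list-maker may measure the primary outcome, which conflicts with section 10.1 and leaves enrolment order and the T0 and T1 readings open to influence. It rests on reading investigator and principal investigator as one role, which the documents support but do not state, and on the list-maker being able to recall or consult the list.

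The resulting bias cannot be sized from the documents. For scale only, the planned difference in 10.4 is 3.0°, so each 1° of differential shift in the readings would be 1/3.0, a third of it. That is not an estimate of what will happen.

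Block size is a secondary matter. A reader might infer that the size of two is the main fault and that removing it would cure the problem; the figures do not support that. Naming the sizes in the protocol does help a guesser (about 70% against 50% by chance, with equally likely sizes assumed), so withholding them is sensible.

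**What to change.** In section 10.5, assign list generation, custody of the list and preparation of the envelopes to an existing team member who neither enrols nor measures, and say so. Keep the block sizes out of documents held by recruiting and measuring staff. In sections 10.1 and 11, state that no one with access to the list measures at T0 or T1.

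A related route stays open if only the list is moved. The weekly log-book check in the intervention arm reveals the arm, so whoever does it should not measure at T1. That can be settled in the same amendment.

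Using sizes 4, 6 and 8 is optional and gains little. It allows an end-of-trial imbalance of up to 8/2 = 4 participants, against 6/2 = 3 with the sizes now named.

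The cost is a small change in who does which task, with no extra participants or visits.

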## **10. Methods of statistical analysis**

The data will be analyzed according to intention to treat. Descriptive statistics will be used to explore the characteristics of the elderly.

The primary outcome is the change in the angle of kyphosis. The secondary outcomes are the score change of pain and self-image, the change in score of the Farsi version of Functional Gait Assessment, change in time of the Timed Up and Go Test and the One Leg Standing Test, change in walking distance of the Six Minutes Walking Test, and change in length of the Chest Expansion test.

T-test and Chi-square test will be used to determine any baseline differences among two intervention groups and one control group in terms of baseline socio-demographics, regular exercise type and intensity, illness condition, and the angle of kyphosis.

Linear mixed effect model will be conducted to explore the between-group and within-group differences in the outcomes across the time, while controlling socio-demographics, illness condition, BMI, type and intensity of regular exercise. SPSS version 23.0 was used to analyze data collected, the significance level will be 0.05.

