### **6.1 Spine measurements (Primary outcome)**

The angle of kyphosis will be measured by manual inclinometer in the proposed study. There are two reasons we do not use X-ray, the gold standard. First, the study will be conducted in community centres without access to the X-ray facilities. Second, the participants will accomplish the angle of kyphosis measurement in two postures in three time points within 12 weeks. Manual measurements can protect the participants from exposing to unnecessary radiation.

Manual inclinometer is have previously demonstrated excellent levels of inter-rater ( $ICC=0.90$ ), and intra-rater reliability ( $ICC=0.92$ ) (Barrett, McCreesh, & Lewis, 2013), and satisfied concurrent validity ( $r=0.86$ ) (Barrett, Lenehan, O'Sullivan, Lewis, & McCreesh, 2018).

The angle of kyphosis will be measured in two conditions, once in participants standing relaxed, once in participants stand as straight as possible. The measurement procedure is as follow: 1) the researcher explaining measuring instructions; 2) participants exposing upper body in two standing posture; 3) identifying and marking the spinous processes of C7, T1, T2, T12, and L1 in two postures; 4) using manual inclinometers measure the angle in two postures. The measurements will also be performed three times in succession.

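### The plan specifies no adjustment of the treatment comparison for the baseline kyphosis angle, and names neither posture nor visit for the primary outcome

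*Combined protocol and SAP*

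**What the plan says.** All references are to the combined protocol and SAP.

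- **Outcome** (10. Methods of statistical analysis): "The primary outcome is the change in the angle of kyphosis". No posture or visit is attached.
- **Model** (same section): "Linear mixed effect model will be conducted to explore the between-group and within-group differences in the outcomes across the time".
- **Covariates** (same section): the model is fitted "while controlling socio-demographics, illness condition, BMI, type and intensity of regular exercise". The baseline angle is not among them.
- **Baseline angle** (same section): it is listed only for the t-tests and chi-square tests that compare groups at baseline, "in terms of baseline socio-demographics, regular exercise type and intensity, illness condition, and the angle of kyphosis".
- **Measurement** (6.1 Spine measurements): the angle is taken "once in participants standing relaxed, once in participants stand as straight as possible". The same section says that "the participants will accomplish the angle of kyphosis measurement in two postures in three time points within 12 weeks" and that "The measurements will also be performed three times in succession".
- **Visits** (10.5 Procedures): the baseline assessment, T0, precedes randomisation to one intervention group or one control group. The text defines one later assessment, T1, after the 6-week intervention. Figure 1 is not shown.

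**The concern.** The pre-randomisation value of the outcome is usually its strongest predictor, and this trial already collects it. The listed covariates are likely to predict the angle less well. A change score uses the baseline, but with a fixed coefficient of one, which is less efficient than estimating the coefficient. A mixed model with T0 and T1 as responses and a free group difference at T0 does no better: with two visits and complete data, its group-by-time estimate is the difference in mean change. Randomisation keeps either analysis unbiased, so the stake is precision.

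The second gap concerns the definition of the primary result. With two postures, an uncertain number of visits and none of them named, the result reported as primary could be settled after the data are seen. The background section shows that posture matters: one cited study of a related exercise programme found a 6° decrease in relaxed standing and 5° in best standing.

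**Working it through.** **The plan's own figure.** Section 10.4 gives an effect size of 0.44 (3.0°), level 0.05, power 0.8, 20% drop-out and 78 per group. A one-sided t-test needs 65 per group, and 65 × 1.2 = 78, which reproduces it. A two-sided test needs 83, or 83/0.8 = 104 recruited. Sidedness is not stated and is a separate matter; the two-sided test below is only for illustration.

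**Inputs.** Completers: 78 × 0.8 = 62 per group. Effect size d = 0.44. T0-T1 correlation ρ = 0.5 / 0.7 / 0.9, assumed because the documents give none. The plan's other covariates are ignored.

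**Variance.** With angle SD σ at both visits, the change score has variance 2σ²(1−ρ) and the baseline-adjusted comparison σ²(1−ρ²). The ratio is (1+ρ)/2 = 0.75 / 0.85 / 0.95. The same precision without adjustment would take 62/ratio = 83 / 73 / 65 completers per group.

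**Power (non-central t, 62 per group).** Section 10.4 does not say which SD the 0.44 refers to, so both are shown.

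| Reading of 0.44 | Analysis | Standardised effect | ρ = 0.5 | ρ = 0.7 | ρ = 0.9 |
|---|---|---|---|---|---|
| SD of change | change score | 0.44 | 0.68 | 0.68 | 0.68 |
| SD of change | baseline-adjusted | 0.44/√((1+ρ)/2) | 0.80 | 0.75 | 0.70 |
| SD of angle | change score | 0.44/√(2(1−ρ)) | 0.68 | 0.88 | 1.00 |
| SD of angle | baseline-adjusted | 0.44/√(1−ρ²) | 0.80 | 0.93 | 1.00 |

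**Entry cut.** Section 10.2 admits only angles above 40°. If T0 is also the screening reading, the cut narrows the T0 spread. Assume normal angles with 72% above the cut (the prevalence in the background section, taken to use the same cut).

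- The cut lies at −0.583 SD and the mean of those above it at 0.468 SD, so the T0 variance factor is v = 1 − 0.583 × 0.468 − 0.468² = 0.509.
- The variance ratio becomes (1−ρ²)/((1−ρ²) + (1−ρ)²v) = 0.855 / 0.918 / 0.974.
- On the SD-of-change reading, adjusted power is 0.75 / 0.72 / 0.69.
- Here ρ is the correlation before selection. Among participants it is ρ√v/√(ρ²v + 1 − ρ²) = 0.38 / 0.57 / 0.83, which is what trial data would show.

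**A check for the sponsor.** The implied SD is 3.0/0.44 = 6.8°. If that is the SD of change, the angle SD is 6.8/√(2(1−ρ)) = 6.8° / 8.8° / 15.2°, ignoring the entry cut. The earlier cross-sectional study can show which is plausible.

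**Posture and visit.** Section 6.1 has two postures and three time points; section 10.5 has T0 and one follow-up; the analysis section selects among none of them.

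**The case against.** **T0 may already be in the model.** A mixed model of outcomes over time, with within-group differences, is naturally read as carrying T0 as a repeated response. This stands: a reader might infer that the model ignores the baseline altogether, and the text does not support that. What the text shows is a covariate list without the baseline angle and no statement that the T0 means are held equal. Without that constraint, a T0 response recovers none of the precision at issue.

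**The starting power of 0.68 is not the planned analysis.** It is an unadjusted t-test on change. This also stands. If the listed covariates explained 10% of the variance of change (an assumption), the starting power would be 0.73, and the increment from baseline might differ. The figures illustrate scale only.

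**The visit can be inferred.** The readable text defines only T1 after baseline, and Figure 1 might settle the matter. That weakens the visit gap but does not close it, because section 6.1 gives a different count. Section 10.3 also describes weekly classes over five consecutive months beside a 6-week intervention period, which bears on what post-intervention means; these passages must be reconciled.

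**The contrast is clear enough.** The research question and the sample size both compare with control, and the model statement names between-group differences first. Largely accepted; the hypotheses' missing comparator is a matter of wording.

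**Conclusion.** The point holds as a recommended improvement and does not challenge validity. As written, the comparison is unbiased under randomisation but gives up precision.

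- **If 0.44 is on the SD of change:** the loss is about 12 / 7 / 2 points of power at assumed correlations of 0.5 / 0.7 / 0.9, and less if the entry cut narrows T0.
- **If 0.44 is on the SD of the angle:** the loss is about 12 / 5 / 0 points.

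A reader might infer that two-sided power must stay below 0.8 after adjustment when the correlation is high. That holds only on the SD-of-change reading.

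The missing posture is certain in the text available. The missing visit is likely but depends partly on a figure not shown. A reader might also infer an inflated false-positive rate, about 9% / 8% / 7% for test correlations of 0.5 / 0.7 / 0.9 if either posture could count at 0.05. The plan does not say that either may count, so this is a risk left open and not a stated rule.

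**What to change.** 1. **Baseline.** Either enter the same-posture baseline angle as a covariate, with post-baseline angles or change as the response, or keep T0 as a response with its means constrained equal across groups. Use one, not both. Do the same for the secondary outcomes.
2. **Primary outcome.** Before analysis, name one posture and one post-baseline visit, both the sponsor's choice. Make the between-group difference there the single primary test and treat the other posture as secondary.
3. **Visits.** Reconcile the time points in section 6.1 with T0 and T1 in section 10.5.
4. **Wording clarifications only.** State how the three successive readings are combined, add the comparator to the hypotheses, and correct the baseline test's reference to "any baseline differences among two intervention groups and one control group", since section 10.5 has one intervention group.

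The cost is wording: no new measurements or participants. The downside is that the other posture can no longer serve as the primary result. The precision gain may also be small if the correlation is high.

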## **11. Describe any unusual or discomforting procedures to be used**

Exposing the upper body in spine measurement may be embarrassing for some participants. In order to protect their privacy, the participant will be invited to a private room with air-conditioned, one at a time. The principal investigator and well-trained researcher helpers will perform the measurement. And the participants can stop measuring whenever they want to. For the measurement of physical fitness, participants may be tired. They can take a rest whenever they need.

In kyphosis-specific exercise class, the instructor participants ratio will be no less than 1:5 to endure the participants' safety. During exercise class, the participants can rest whenever they think is necessary. The first aid equipment will

be prepared. In the video exercise group orientation, the investigator will give exercise safety instruction.

Most of the exercises including in the kyphosis-specific exercise video are taking supine or prone posture, in order to prevent fall during exercise. In every follow up kyphosis-specific exercise classes, the certified physical trainer will reinforce safety instructions and exercise skills. The participants will be encouraged to contact the investigator whenever they have questions. No serious adverse event was reported by the previous studies letting older adults following exercise video doing home exercise.

